The protocol, informed consent forms (ICF), recruitment materials, and all participant materials will be submitted to the IRB for review and approval. Approval of both the protocol and the ICF must be obtained before any participant is enrolled. Any amendment to the protocol will require review and approval by the IRB before the changes are implemented to the study. All changes to the ICF will be IRB approved; a determination will be made regarding whether a new ICF needs to be obtained from participants who provided consent, using a previously approved ICF. Informed consent will be administered electronically (e-consent) in this study via a hand-held device.

1 PROTOCOL SUMMARY

1.1 SYNOPSIS

Title:	A Phase IB Dose Escalating Study of the Safety, Short-Term Engraftment and Action of a Singly Applied NB01 in Adults with Moderate Acne
Study Description:	
Acne vulgaris is a multifactorial disease caused by overgrowth of Propionibacterium acnes (P. acnes), impaction of hair follicles, excessive sebum production and hormonal dysregulation. Recent literature from the Human Microbiome Project has shown there are unique microbial signatures specific to healthy and acne disease states (Fitz-Gibbon et al. 2013), (Tomida et al. 2013). Subsequent literature discovered a repressor in the porphyrin pathway in health-associated strains resulting in significantly lower porphyrin production (Johnson et al. 2016). Porphyrin is a known inflammatory mediator in acne pathogenesis (Kang et al. 2015). Porphyrin levels inversely correlate with therapeutic improvement in acne (Richter et al. 2016). Additional papers have highlighted other virulent factors such as the pIMPLE plasmid that may be associated with acne pathogenesis and were found to be more common in disease-associated strains (Kasimatis et al. 2013).
 
From this data, we hypothesize that by eliminating resident disease-associated bacterial strains and replacing them with a health-associated P. acnes transplant, we may be able to improve, mitigate, treat clinical disease (acne) and prevent recurrences/flares of said disease. Instead of current approaches which focus on eliminating all bacteria from the skin, we aim to deliver healthy bacteria to restore the skin to a healthy state via this replacement therapy.
 
We aim to test this in a Phase Ib single application study evaluating the safety, tolerability, and clinical impact that a single application of a P. acnes transplant, hereafter referred to as NB01, has on adult subjects with moderate acne. We want to profile the change in microbiome over the course of therapy to determine if exogenously delivered bacteria can populate the skin (engraftment) and cause a shift in the microbiome safely and subsequently impact acne

	
biomarkers (porphyrin) that may correlate with clinical disease.
 
Engraftment measurements would be more challenging to obtain in healthy individuals in which we would be trying to replace a healthy microbiome with a healthy microbiome. Our product is low risk, using bacteria native not only to human skin, but to the pilosebaceous units of the face, and P. acnes makes up 90% of the bacteria on the skin in both diseased and healthy individuals (Fitz-Gibbon et al. 2013), (Tomida et al. 2013).
 
We intend for this therapy to eventually be used in acne subjects with ages ranging from 13-40, and all disease severities as either monotherapy for mild to mild/moderate acne and as an adjuvant therapy for moderate to severe acne at all body sites, with special attention to facial involvement.
 
This approach is standard to acne therapy whereby mild disease will be treated with a monotherapy (i.e., 5.0% Benzoyl peroxide [BPO]) and moderate/severe disease will be treated with various combinatory regimens (topical antibiotics, 5.0% BPO, topical retinoids, oral antibiotics).

Objectives:	
Primary Objectives:
 
 1. To determine the safety profile and tolerability of a singly applied NB01 2. To define engraftment of a singly applied topical NB01 3. Dose schedule determination based on engraftment 
Secondary Objective: To evaluate clinical efficacy using Investigator Global Assessment (IGA) and acne lesion counts of a singly applied NB01 (FDA [Food and Drug Administration] Guidance for Industry: Acne Vulgaris, Developing Drugs for Treatment)
 
Exploratory Objective: To evaluate biomarkers of treatment effects, including but not limited to porphyrin production, sebum production, and pH

Study Population:	Approximately 10 male and female adult subjects combined with moderate, non-cyclical acne will be enrolled into the trial. Approximately five (5) subjects will be assigned to each dose schedule (either 10^5 CFU/cm ² or 10^6 CFU/cm ²).
Phase:	Ib
Description of Sites/Facilities Enrolling Participants:	This study will be conducted at 1 center in the state of California, within the US, under the direction of [name].
Description of Study Intervention:	This is a single topical application study of a live bacteria for the study of acne in adult subjects.
Subject/Study Duration:	Subject participation in the trial will be approximately 5 weeks. Approximately 1 week pre-treatment with a daily 5.0% BPO gel 1 month of study drug: single application and 28-day follow up

1.2 SCHEDULE OF EVENTS (SOE)

Schedule of Events (SOE) - Single Application (Phase IB): NB01-P1BSA

STUDY PERIOD ►	Baseline	Treatment						End of Study
STUDY DAY (± visit window) ►	Day -5	0H (+2 days)	6H (±2 hrs)	24H (±2 hrs)	48H (±2 hrs)	7 days (±1 day)	Unscheduled Visit ⁿ	28 days ^o (±3 days)
PROCEDURE ▼ TREATMENT DAY ►	Screening	Day 1 ^b	Day 1	Day 2	Day 3	Day 7	NA	Day 28/EOS
Eligibility Criteria Review ^a	X							
Electronic Informed Consent Process	X							
Medical History	X							
Concomitant Medication Review	X	X	X	X	X	X	X	X
Directed PE ^c	X	X					X	
Cheek Swab Engraftment Sample (TaqMan® Assay)	X ^f	X	X	X	X	X	X	X
Vital Signs ^{d, e}	X			X		X	X	X
Laboratory Assessment - CBC ^d	X						X	
Pregnancy Test (urine dipstick) ^g	X	X					X	X
BPO 5.0% gel application	X ^h							
Electronic Patient Diary	X ⁱ	X	X	X	X	X	X	X
Enrollment	X							
AE Assessment	X ^k	X ^j	X	X	X	X	X	X
Assess Porphyrin Levels (Pear 3D)	X	X	X	X	X	X	X	X
Sebum Production Measurement (Pear 3D)	X	X	X	X	X	X	X	X

Schedule of Events (SOE) - Single Application (Phase IB): NB01-P1BSA (concluded)

Skin pH measurement (Skin pH Meter)	X	X	X	X	X	X		X
Assess Follicular Engraftment via Bioré® Strip (TaqMan® Assay)	X			X				
Investigator Global Assessment (IGA)	X	X	X	X	X	X	X	X
Absolute Lesion Count	X	X	X	X	X	X	X	X
Photography (Pear 3D)	X	X	X	X	X	X	X	X
Facial Cetaphil® Washing	X ^{p,q}	X ^{l,m}	X	X	X	X	X	X
Investigator Assessment of Tolerability	X	X	X	X	X	X	X	X
Single NB01 application (by Investigator)		X						

Abbreviations: AE = Adverse Event; BID = Twice Daily; BPO = Benzoyl Peroxide; CBC = Complete Blood Counts; EOS = End of Study; PE = Physical Examination.

^a Includes confirmation of contraception use for the duration of Screening prior to first application and through study participation; Principal Investigator (PI) should assess subject eligibility after e-consent and prior to remaining screening period procedures.

^b All Day 1 baseline procedures must be completed prior to the PI application of NB01 at Time Point 0 (T0H).

^c Limited PE of face, chest, arms, back (relevant acne regions).

^d Vital signs and CBC assessed at Screening Visit, prior to initiation of BPO pre-treatment. Vital signs and CBC are only repeated if clinically warranted.

^e Blood pressure, heart rate, temperature.

^f Screening sample to be obtained prior to initiation of BPO pre-treatment.

^g Urine dipstick test, assessed locally.

^h BPO gel should be applied for at least 5 days, in the AM immediately after the AM Cetaphil® wash. Final BPO pre-treatment should be completed at least 24 hours prior to PI application of NB01, thus final BPO application will most likely occur in the AM prior to the Day 1 (0H) visit.

ⁱ Trial subjects will note date and time of each BPO pre-treatment and Cetaphil® wash for the Screening period, and the date and time for each Cetaphil® wash during the 28-day treatment period.

^j Subjects will remain at the clinic for at least 30 minutes post application at T0H to be assessed for adverse reactions.

^k AEs will be assessed from the time of e-consent.

^l On Day 1, after baseline measurements have been obtained, subjects will then wash at the clinic before NB01 is applied by the PI.

^m Subjects initiate BID washing of their faces after waiting 24 hours from T0H, or 24H (Study Day 2). Subjects should withhold morning wash and morning facial shaving at home until they arrive at the clinic all clinic days. Once clinic day sampling has occurred, the subject may wash at the clinic. The only exception being that the subject should wash their face in the office with Cetaphil®, prior to the Day 2 Bioré® Strip follicular engraftment sampling

ⁿ Study procedures are completed as needed, as clinically indicated, for unscheduled study visits.

^o The EOS Visit should be completed on Day 28, or prior to the initiation of new anti-acne therapy. Should the subject discontinue the study early, the EOS should be scheduled and completed as soon as possible.

^p No other cleansers can be used throughout the study, from the Screening Visit to Day 28/EOS.

^q Subjects will hold the PM Cetaphil® wash prior to the Day 1 study drug application.

2 INTRODUCTION

2.1 STUDY RATIONALE

Acne vulgaris is a multifactorial disease affecting 85% of the global population over a lifetime and 40-50 million US people in the US currently. It impacts individuals over a large timespan ranging from 13-40 years, and has a large psychosocial impact on an individual's self-esteem. The majority of those afflicted (50%-75%) are now resistant to conventional antibiotic therapy (Walsh et al. 2016). Acne is caused by overgrowth of *P. acnes*, impaction of hair follicles, excessive sebum production and hormonal dysregulation. Current standard of care includes treatment with 5.0% BPO, retinoids, and antibiotics. However, there are significant side effects of the above medications, limiting subject compliance and leading to suboptimal long-term efficacy. The heavy dependence on long treatment courses of antibiotics combined with antibiotic resistance rising upwards of 50%-75%, is resulting in treatment failures and contributing to overall global antibiotic resistance. There has been little innovation in acne therapy in the past several decades and a significant current need to develop antibiotic alternatives.

Current therapeutic options include:

- Topical antibiotics-erythromycin/clindamycin-high resistance
- Oral Antibiotics-tetracycline (doxycycline, minocycline)-high resistance
- Topical 5.0% BPO products-irritating, drying, redness
- Topical retinoids-irritating, drying, photosensitivity, peeling,
- Oral Retinoids-high side effect profile, Ipledge system, cumbersome for subjects
- Topical acids-salicylic acid, glycolic acid
- Peels-subject out of pocket expense, not reimbursable
- Laser-Blue and red-light therapies-subject out of pocket expense, not reimbursable
- Dapsone (Aczone®)-minimal additional benefit over existing topical regimens
- Azelaic acid (Finacea®)-minimal additional benefit over existing topical regimens
- Microdermabrasion-subject out of pocket expense, not reimbursable

Recent literature from the Human Microbiome Project has shown there are unique microbial signatures specific to healthy and acne disease states (Fitz-Gibbon et al. 2013), (Tomida et al. 2013). Subsequent literature discovered a repressor in the porphyrin pathway in health-associated strains resulting in significantly lower porphyrin production (Johnson et al. 2016). Porphyrin is a known inflammatory mediator in acne pathogenesis (Kang et al. 2015). Porphyrin levels inversely correlate with therapeutic improvement in acne. (Richter et al. 2016). Additional papers have highlighted other virulent factors such as the pIMPLE plasmid that may be associated with acne pathogenesis and were found to be more common in disease-associated strains (Kasimatis et al. 2013).

From this data, we hypothesize that by eliminating resident disease-associated bacterial strains and replacing them with a health-associated *P. acnes* transplant, we may be able to improve, mitigate, treat, or prevent acne flares. We aim to test this in an initial Phase I evaluating the safety, tolerability, and clinical impact that a single dose application of NB01 has on adult subjects with moderate acne.

This initial study will be a Phase Ib single center open label dose escalation study using a single dose application with monitoring over 28 days on 10 subjects at 2 different concentrations (lower bound and upper bound). If we meet the safety criteria of this initial study, we plan to expand the IND research to a Phase Ib multi-dosed study. All subjects will be pre-treated with a daily 5.0% BPO gel (<https://www.perrigo.com/business/product.aspx?ID=88&let=B> Perrigo 5% BP Aqueous Gel) to decrease their resident microbiome bacterial load in preparation for transplantation and successful repopulation with a healthy microbiome.

2.2 BACKGROUND

We hypothesize that by eliminating resident disease-associated bacterial strains and replacing them with a health-associated *P. acnes* transplant, we may be able to improve, mitigate, treat, or prevent acne flares. We aim to test this in an initial Phase I evaluating the safety, tolerability, and clinical impact that a single dose application of NB01 has on adult subjects with moderate acne.

Our genotypic and phenotypic work identified candidate strains sourced from healthy subjects that match all our criteria for health. Genotypically, our candidate strain is a *P. acnes* ribotype 2, deoR+, lipase type II+, contains a complete CRISPR system, is absent the pIMPLE plasmid, and has no identifiable genomic evidence of antibiotic resistance. Phenotypically, our candidate strain produces low levels of porphyrin, comparable to other healthy associated ribotype 2's in the literature and was sensitive to all 5 antibiotics tested internally (Clindamycin, Doxycycline, Erythromycin, Minocycline, Tetracycline as was measured with Etest (bioMérieux).

Additional safety assessment report was performed by CHR-Hansen, Naked Biome's GMP manufacturer, who confirmed that no genomic antibiotic resistance genes were present and that our strain was sensitive to 13 out of 14 tested antibiotics, resistant only to metronidazole which *P. acnes* has known natural resistance to, and was additionally non-hemolytic and non-cytotoxic.

There is no *in vivo* data to date on the safety or clinical efficacy of a topical live *P. acnes* microbiome transplant. As described in our Pre-IND meeting, there are no well substantiated animal models for inflammatory acne and we are working with human-specific bacteria. Therefore *in vivo* animal clinical and toxicology studies will not yield clinically relevant results that would be applicable for human use. Sponsor rationale, in accordance with FDA correspondence, is that animal clinical and toxicology studies are not relevant or useful when we are using human-specific bacteria absent well-substantiated animal models for inflammatory acne for pre-human efficacy testing (Mirshahpanah and Maibach 2007). The best, most relevant, and only useful model to test our lead drug candidate is first in humans (Mirshahpanah P, Howard Maibach 2007), (Achermann et al. 2014). Additional literature on previous human studies for probiotics and acne are listed in the following references (Baquerizo et al. 2014), (Wei et al. 2016), (Thiboutot et al. 2009).

Outside of known association of *P. acnes* with acne vulgaris, below is an accrued list of rare opportunistic infections associated with *P. acnes*. *P. acnes* has been observed in other infections such as implant-associated infections, soft tissue, periodontal, periocular, cardiovascular system, deep-organ tissues infections, and may also have a role in relation to pulmonary infection as the bacteria can be isolated from lungs and lymph nodes. Routes of infection is often from the subject own commensal flora (normal skin or oral tract) (Whitman et al. 2012), (Kwon and Suh 2016). The expanded multi-locus sequence typing scheme based on 7 housekeeping genes and 2 putative virulence genes developed by McDowell et al gives a good resolution and revealed CC types which seem to have an increased capacity to cause infections and others that are rarer or found mainly among healthy individuals. (McDowell et al. 2012), (McDowell et al. 2013).

Strain HP4G1 contains the deoR repressor gene, and thus may not be associated with acne. Further, the strain has a PAp60/PAmce allele combination found in non-invasive *P. acnes* strains and lacks 2 of 4 genes involved in iron uptake, which is of importance for growth in the human body at conditions with low iron access. Notably, regarding CAMP factors 1-4, which are expected to be involved in pathogenicity and are involved in co-hemolysin with *Staphylococcus aureus* (*S. aureus*), HP4G1 had a mutation in the CAMP 2 gene leading to an extension of the gene as the stop codon was interrupted. This variant has not been observed before and as CAMP factor 2 is described as having properties for co-hemolysin and exotoxin, this may lower the pathogenic potential of the strain. Moreover, the strains belong to the CC72 clonal complex which, compared to CC5, contains strains less commonly isolated from healthy humans or individuals with infections. HP4G1 was found to be a ST100-like type not previously reported and most likely has a non-functional CAMP2 gene due to a mutation in the stop

codon. Therefore, HP4G1 is most likely less virulent than *P. acnes* in general with a low risk of causing infections.

Porphyrin is a known inflammatory metabolite involved in the pathogenesis of acne. Porphyrin is produced by the *P.acnes* bacterium and is a photosensitizing agent. Dermatologists routinely use blue and red light therapies to selectively target *P.acnes*-produced coproporphyrin III and protoporphyrin IX, respectively, thereby eliminating *P.acnes* and improving disease. As stated above, HP4G1 has a repressor of porphyrin production, called *deoR*. *In vivo*, the HP4G1 strain produces less porphyrin than acne-associated strains that lack the *deoR* repressor operon. Despite that the HP4G1 strain is a low porphyrin producer, the fact that it is applied in significant quantities (10^5 CFU/cm²) and (10^6 CFU/cm²), could lead to a temporary increase in porphyrin upon application. This hypothetical increase could be photosensitizing to subjects, as such, photosensitivity has been included as a theoretical side effect of HP4G1 application.

We are addressing the risk of these opportunistic infections through the selection of genotypic and phenotypic characteristics most associated with health and with the implementation of appropriate exclusion criteria to eliminate subjects that may have increased risk of a *P. acnes* infection.

Exclusion Criteria addressing above

1. Active bacterial, viral, or fungal skin infections.
2. Any noticeable breaks or cracks in the skin on the face, including severely excoriated skin or skin with open or weeping wounds suggestive of an active infection or increased susceptibility to infection.
3. Comorbid skin conditions in the area of application.
4. Active periodontal disease or ongoing procedures (e.g., gum grafting).
5. History/current ocular infections/surgeries within 6 months of enrollment, with the exception of any history of cataracts.
6. History of sarcoidosis.
7. History septic joints/endocarditis.
8. Participants with Netherton's syndrome or other genodermatoses that result in a defective epidermal barrier.
9. Sensitivity to or difficulty tolerating glycerin, polyethylene glycol.
10. History of isotretinoin use, with the exception of sub-therapeutic treatment within 8 weeks of enrollment.
11. Less than 80% compliance with pre-treatment BPO, or less than 5 days' worth of BPO pre-treatment (whichever is greater) during the Screening period.
12. Current major systemic comorbid conditions.
13. Currently participating in (or within 8 weeks of enrollment) in another acne trial or other investigational drug.
14. Participants with prosthetic heart valves, pacemakers, intravascular catheters, or other foreign or prosthetic devices/implantable devices/hardware.
15. Participants with close contact (e.g., spouses, children, or members in the same household) with prosthetic heart valves, pacemakers, intravascular catheters, or other foreign or prosthetic devices/implantable devices/hardware.
16. Known chronic human immunodeficiency virus (HIV), hepatitis C virus (HCV), or hepatitis B virus (HBV) infections.
17. History of malignancy (with the exception of non-melanoma skin cancer).
18. Immunosuppression (such as resulting from transplantation, immunosuppressive therapy, active HIV infection/acquired immune deficiency syndrome [AIDS], neutropenia).
19. Major surgical procedure, open biopsy, or significant traumatic injury within 14 days of initiating study drug (unless the wound has healed), or anticipation of the need for major surgery during the study.

20. The presence of a medical or psychiatric condition, history of drug or alcohol abuse that, in the opinion of the PI, makes the subject inappropriate for study inclusion.
21. Participants with close contacts (e.g., spouses, children, or members in the same household) that have severe barrier defects or are immunocompromised.
22. Inability or unwillingness of participant to comply with study protocol procedures.
23. Pregnant or lactating females, or females who desire to become pregnant and/or breast feed within the duration of study participation.
24. Imprisonment or under legal guardianship.

As was discussed at our Pre-IND meeting, *P. acnes* is most specific to facial pilosebaceous region and is the natural niche for *P. acnes*, and therefore the best region for application to appropriate the sensitivity and therapeutic impact of a topical *P. acnes* transplant (McGinley et al. 1980).

3 OBJECTIVES AND ENDPOINTS

OBJECTIVES	ENDPOINTS	JUSTIFICATION FOR ENDPOINTS
Primary		

 Determine the safety and tolerability of a singly applied NB01 Define engraftment of a singly applied topical NB01 Dose schedule determination based on engraftment 	
Safety Assessments:
 
 Skin Dryness Skin Peeling Irritant/Contact dermatitis Hyperpigmentation Ocular Toxicity Mucosal Toxicity Skin erythema Assessment of Disease Status 
Efficacy Assessments: Engraftment is defined as deoR/PanBac>40% and Cas5/PanBac>40%. Disease associated bacteria are typically deoR, Cas5 negative (Kang et al, 2016), therefore, ratios are expected to be low <10% in acne subjects. The NB01 strain as measured with our TaqMan assays is approximately 100% deoR/PanBac and Cas5/PanBac, so we expect the ratio to increase with successful engraftment. This will help to determine dosing regimen/schedule for multi-dosed trials where the drug will be applied in a frequency to ensure that product levels remain above these parameters. For example, if deoR/PanBac drops to <40% at or before 6 hours then the application will be twice daily (BID); every (Q) 12 hours.
	Disease exacerbation along with erythema, dryness, pigmentation irritant/contact dermatitis, mucosal and ocular toxicity are commonly tested safety endpoints in topical dermatologic trials.
Secondary		
To evaluate clinical efficacy using IGA and acne lesion counts of a singly applied NB01	IGA and acne lesion count	IGA and acne lesion counts are conventional measurements for assessing efficacy in acne trials
Tertiary/Exploratory		
To evaluate biomarkers of	
 Porphyryn and sebum levels 	Porphyryn is a known


treatment effects, including but not limited to porphyrin production, sebum production, and pH
	
as measured using a Pear 3D Analysis System
 
 pH as measured using pH meter 	
inflammatory metabolite in acne pathogenesis and levels have been shown to inversely correspond to therapy (Johnson et al. 2016). Our strains have a repressor for porphyrin production and if our strains engraft, we hypothesize that they will maintain low levels of porphyrin on the face compared to baseline screening levels.
 
Sebum is “food” for P. acnes and we expect high sebum producers to have higher levels of resident bacteria (McGinely et al. 1980).
 
Low pH is more associated with acne and conversion to anaerobic metabolism and porphyrin production (Shu et al, 2013), (Dailey et al 2015), (Kjeldstad et al. 1984).

---	--	---

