We aim to test this in a Phase Ib single application study evaluating the safety, tolerability, and clinical impact that a single application of NB01 has on adult subjects with moderate acne. We want to profile the change in microbiome over the course of therapy to determine if exogenously delivered bacteria can populate the skin (engraftment) and cause a shift in the microbiome safely and subsequently impact acne biomarkers (porphyrin) that may correlate with clinical disease. Health-associated *P. acnes* contain both deoR and Cas5, thus the ratios of deoR/PanBac and Cas5/PanBac is approximately 1 in our formulation. Disease associated *P. acnes* typically lack deoR and Cas 5 (Kang et al, 2016) leading to a deoR/PanBac <10% on acne individuals. We expect an upwards shift in deoR/PanBac and Cas5/Panbac with the application of our strains to acne subjects. Thus, engraftment is defined as deoR/PanBac>40% and Cas5/PanBac>40%. This will help to determine dosing regimen/schedule for multi-dosed trials where the drug will be applied in a frequency to ensure that product levels remain above these parameters. For example, if deoR/PanBac drops to <40% at or before 6 hours then the application will be BID (Q12 hours). Disease-associated strains, in contrast, typically lack deoR and Cas4, but contain transposase2 (TPase2). Subjects will also be profiled with TPase2/PanBac ratios to determine how the pathogenic strain profiles are impacted over time with application of drug, and if there are certain profiles that increase or decrease likelihood of successful engraftment.

Engraftment measurements would be more challenging to obtain in healthy individuals in which we would be trying to replace a healthy microbiome with a healthy microbiome. Our product is low risk, using bacteria native not only to human skin, but to the pilosebaceous units of the face, and *P. acnes* makes up 90% of the bacteria on the skin in both diseased and healthy individuals (Fitz-Gibbon et al. 2013).

We intend for this therapy to eventually be used in all ages of acne subjects ranging from 13-40, and all disease severities as either monotherapy for mild to mild/moderate acne and as an adjuvant therapy for moderate to severe acne at all body sites, with special attention to facial involvement.

This approach is standard to acne therapy whereby mild disease will be treated with a monotherapy (i.e., 5.0% BPO) and moderate/severe disease will be treated with various combinatory regimens (topical

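### Engraftment is defined as an absolute level above 40% with no condition on the 0H swab, so a subject already above it on both ratios before application, and staying there, counts as engrafted with no product effect

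*Combined protocol and SAP*

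**What the plan says.** The primary engraftment endpoint in Section 3 is a level on two ratios: "Engraftment is defined as deoR/PanBac>40% and Cas5/PanBac>40" percent. Section 4.2 gives the same rule. Neither place mentions a pre-application value, a rise, or a visit.

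The markers are not unique to the product. Section 4.2 says that health-associated *P. acnes* "contain both deoR and Cas5, thus the ratios of deoR/PanBac and Cas5/PanBac is approximately 1 in our formulation".

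The low starting point and the rise are stated as expectations. Section 3 says that "ratios are expected to be low <10% in acne subjects" and, of the product's own ratio of about 100%, "so we expect the ratio to increase with successful engraftment". Section 4.2 adds: "We expect an upwards shift in deoR/PanBac and Cas5/Panbac with the application of our strains to acne subjects". The entry criteria in Sections 5.1 and 5.2 rest on clinical grade, lesion counts and exclusions for risk. They set no limit on either ratio.

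Two swabs precede NB01. The Screening swab is taken before benzoyl peroxide (BPO) starts (Section 1.2, footnote f). The 0H swab is taken after BPO and just before application (Section 6.1.1). The definition uses neither. Section 10.1 plans summaries before and after transplant without saying which of the two is the *before* value. Section 10.4.1 plans a tabulation for each subject at each time point.

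Section 3 then uses the result to plan later multi-dose trials, in which "the drug will be applied in a frequency to ensure that product levels remain above these parameters". It illustrates this with the case "if deoR/PanBac drops to <40% at or before 6 hours".

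**The concern.** The plan describes engraftment as a rise caused by the product, but its rule asks only where the ratio ends up. Resident strains can supply the same two markers, so a high ratio after application need not come from NB01.

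Three things make this matter:

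- Engraftment is a primary endpoint, and the third primary objective (dose schedule) is based on it. Section 3 treats the ratio as a measure of product level.
- The trial is open-label with no control arm (Section 6.3). The subject's own 0H value is the only reference taken immediately before application.
- Section 4.2 plans to examine "if there are certain profiles that increase or decrease likelihood of successful engraftment". Under an absolute rule, subjects who already carry more health-associated strains qualify more easily by definition, so an association with starting profile could arise partly from the rule itself.

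**Working it through.** The plan gives no power, alpha or sample-size figure for this endpoint, so there is nothing to reproduce. The check is of the rule itself.

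**Inputs.** Threshold 40% on both ratios (Sections 3 and 4.2). Product ratio about 1 (Sections 3 and 4.2). Expected starting ratio below 10% (Section 3). About 5 subjects per cohort (Section 10.3). Assumptions not in the documents: the swab signal is a simple mixture of product and resident bacteria, and the resident ratio has not changed since 0H.

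**Formula.** Let R0 be the ratio at 0H and f the product's share of the total bacterial signal. Then

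observed ratio = f × 1 + (1 − f) × R0 = R0 + f(1 − R0).

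Setting this to 0.40 gives the share needed to reach the threshold:

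f = (0.40 − R0) / (1 − R0).

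| R0 at 0H | calculation | product share needed |
|---|---|---|
| 0% | 0.40 / 1.00 | 40.0% |
| 5% | 0.35 / 0.95 | 36.8% |
| 10% | 0.30 / 0.90 | 33.3% |
| 20% | 0.20 / 0.80 | 25.0% |
| 30% | 0.10 / 0.70 | 14.3% |
| 38% | 0.02 / 0.62 | 3.2% |
| above 40% | threshold already met | none |

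Within the plan's expected range (0% to 10%) the rule behaves consistently: it implies a product share of 33% to 40%. Outside that range its meaning weakens, and above 40% on both ratios it requires no product at all.

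**Effect of one subject.** In a cohort of 5, one misclassified subject moves an engraftment rate by 1/5 = 20 percentage points.

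**Frequency.** The documents give no distribution of the 0H ratio. For scale only, let p be the assumed chance that a subject starts above 40% on both ratios. The chance of at least one such subject is 1 − (1 − p)^n. For p from 2% to 20% this runs from 9.6% to 67.2% with n = 5, and from 18.3% to 89.3% with n = 10. At p = 0, which fits the plan's expectation, it is zero. These are not estimates for this trial.

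**Which condition on 0H works.** One might exclude only subjects above 40% on both ratios at 0H. Suppose a subject goes from deoR 60% and Cas5 39% at 0H to 45% and 41% later. That condition would count the subject as engrafted although deoR fell. Requiring each ratio to be at or below 40% at 0H removes this case, because both must then have crossed the threshold.

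A move from 38% to 41% would still count, with an implied share of 0.03/0.62 = 4.8%. From a start of 10%, reaching 41% needs 0.31/0.90 = 34.4%. Reporting the change beside the level makes that difference visible.

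**The case against.** The best defence is that the design already deals with this. Sections 1.1 and 4.2 acknowledge that engraftment is hard to measure in people with a healthy microbiome, and the plan responds by enrolling moderate acne and pre-treating with BPO. For deoR, Section 4.2 presents a ratio below 10% as what follows from the strains found in acne. The 40% threshold is at least four times that level. Section 4.2 puts *P. acnes* at 90% of skin bacteria. If only *P. acnes* carries the markers (an assumption), a resident ratio above 40% needs more than 0.40/0.90 = 44% of resident *P. acnes* to carry them. The documents offer no evidence that this occurs in such subjects.

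Reporting is also largely planned. Section 10.1 summarises efficacy endpoints before and after application, and Section 10.4.1 tabulates every subject at every time point and plots primary outcomes. Section 4.2 tracks a marker of disease-associated strains (TPase2) as well. There is no formal test to distort, and Section 10 does not specify an engraftment rate.

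Much of this stands, and it limits the consequence. It does not repair the rule. Choosing the population makes a high starting ratio less likely but checks no individual, and Section 3 itself words the low ratios as an expectation. A listing would show a high 0H value, but the stated definition would still class that subject as engrafted. Any reclassification would then be decided after open-label data had been seen.

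On which swab is the *before* value, usage is mixed. Section 1.2 (footnote b) and Section 5.5 call the Day 1 pre-application procedures baseline, while Sections 3 (exploratory row) and 8.2.2 tie baseline to Screening.

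**Conclusion.** The point holds as a defect in a stated rule and should be fixed before data are seen. A subject above 40% on both ratios at 0H, and remaining there, is classed as engrafted with no product effect. This follows from the definition, the shared markers and the absence of an entry limit. Only the implied product shares depend on the mixture assumption.

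Its practical size is unknown. It is nil if every subject starts below 10%, and up to 20 points on a cohort rate for each subject who does not.

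A reader might infer more than the documents support:

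- That subjects will be misclassified. The documents give no frequency of high starting ratios, and their own expectation implies none.
- That a deoR ratio alone will fix the later schedule. The 6-hour sentence in Section 3 is an example. The sentence before it refers to both parameters and says only that the result will help to determine the schedule.
- That dose escalation is compromised. Sections 4.1, 8.1 and 11.1.6 base escalation on dose-limiting toxicities and safety review, not on engraftment.

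**What to change.** Change the wording in Sections 3, 4.2 and 10:

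1. Name the 0H swab (post-BPO, pre-application) as the reference for swab engraftment and as the *before* value for engraftment in Section 10.1.
2. Count a subject as engrafted at a post-application visit only if both ratios exceed 40% at that visit and each was at or below 40% at 0H.
3. List subjects above 40% on either ratio at 0H separately, as not assessable for yes/no status, with their change from 0H.
4. Report each subject's 0H ratios and change from 0H beside the absolute level at every visit. State that each swab covers one facial quarter (Section 8.1), so change can include between-quarter variation. Section 1.2 schedules seven swabs over four quarters, so quarters repeat, but compared swabs may or may not share one.

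The cost is wording only, because the 0H swab is already collected. The downside is that a subject with a high 0H ratio gives no yes/no result, in cohorts of about 5. The fix has two limits. It does not make the markers product-specific, so a later shift among resident strains could still contribute. It also cannot be applied to the follicular strip, which Section 1.2 schedules only at Screening and 24H.
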